### 4.2 Study Endpoints

#### 4.2.1

#### Primary Study Endpoints

The primary endpoint will be percentage of patients remaining on Envarsus XR at 1-year follow-up.

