#### **5.7.2 Termination**

#### **Handling of Participant Withdrawals or**

In the event a patient requests to withdrawal or is terminated from the study, the patient will either be continued on Envarsus XR or converted back to IR tacrolimus at the discretion of the transplant pulmonologist. If a patient withdrawals from the trial due to a hypersensitivity or severe adverse reaction to tacrolimus, future anti-rejection regimen will be determined by the transplant pulmonologist.

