## **10.3 Analysis Datasets**

All subjects will be entered into a database containing de-identified information. All patients who take one dose of the study drug will be included in the safety analyses (intention-to-treat). However, only patients completing the full first year post-lung transplant will be included in the efficacy analysis (per-protocol analysis).

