### **10.4.2**

#### **Analysis of the Primary Efficacy Endpoint(s)**

The primary endpoint, percentage of patients remaining on Envarsus XR at 1-year, will be measured as a single endpoint on a nominal scale. It will be analyzed using descriptive statistics.

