### **10.4.4**

#### **Safety Analyses**

Safety endpoints include worsening chronic kidney disease and discontinuation of therapy will be analyzed as changes from baselines and summary data during the course of treatment, respectively. These will be compared as linear regression and frequencies using the chi-square test, respectively. All AEs will be ascertained and reported by the PI.

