### **13.4 Participant and Data Confidentiality**

Information about study subjects will be kept confidential and managed according to the requirements of the Health Insurance Portability and Accountability Act of 1996 (HIPAA). Those regulations require a signed subject authorization informing the subject of the following:

- What protected health information (PHI) will be collected from subjects in this study
- Who will have access to that information and why
- Who will use or disclose that information
- The rights of a research subject to revoke their authorization for use of their PHI.

In the event that a subject revokes authorization to collect or use PHI, the investigator, by regulation, retains the ability to use all information collected prior to the revocation of subject authorization. For subjects that have revoked authorization to collect or use PHI, attempts should be made to obtain permission to collect at least vital status (i.e. that the subject is alive) at the end of their scheduled study period.

Participant confidentiality is strictly held in trust by the participating investigators, their staff, and the sponsor(s) and their agents. Therefore, the study protocol, documentation, data, and all other information generated will be held in strict confidence. No information concerning the study or the data will be released to any unauthorized third party without prior written approval of the sponsor.

The study monitor, other authorized representatives of the sponsor, representatives of the IRB or pharmaceutical company supplying study product may inspect all documents and records required to be maintained by the investigator, including but not limited to, medical records (office, clinic, or hospital) and pharmacy records for the participants in this study. The clinical study site will permit access to such records.

The study participant's contact information will be securely stored at the site for internal use during the study. At the end of the study, all records will continue to be kept in a secure location for as long a period as dictated by local IRB and Institutional regulations.

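### The primary retention percentage has no stated denominator, and a literal reading puts it in first-year completers, which drops patients who die and raises the figure

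*Combined protocol and SAP*

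**What the plan says.** Section 4.2.1 states: "The primary endpoint will be percentage of patients remaining on Envarsus XR at 1-year follow-up". Section 10.4.2 adds little: "The primary endpoint, percentage of patients remaining on Envarsus XR at 1-year, will be measured as a single endpoint on a nominal scale", to be summarised descriptively. Neither says who is in the denominator or how deaths, losses and withdrawals count. Section 10.1 says no formal SAP is needed, so no later document is planned to settle it.

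Section 10.3 defines two sets. For safety: "All patients who take one dose of the study drug will be included in the safety analyses (intention-to-treat". For efficacy: "only patients completing the full first year post-lung transplant will be included in the efficacy analysis (per-protocol analysis". Retention is described under the heading "Analysis of the Primary Efficacy Endpoint(s".

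Three other places bear on the point:
- Section 10.4.4: "Safety endpoints include worsening chronic kidney disease and discontinuation of therapy".
- Section 5.7.2, on patients who withdraw or are terminated: "the patient will either be continued on Envarsus XR or converted back to IR tacrolimus at the discretion of the transplant pulmonologist".
- Section 13.4, on patients who revoke authorization: "attempts should be made to obtain permission to collect at least vital status".

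On survival, section 5.1 admits controls only if they completed a year from transplant on IR tacrolimus, and section 10.5 describes the cohort in the same way. Section 10.4.3, item 6, plans a Kaplan-Meier and log-rank comparison of 1-year mortality.

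**The concern.** Section 3.1 sets feasibility of early conversion as the primary objective. A patient who starts Envarsus XR and dies within the year is part of that experience and cannot be on the drug at 1 year. If the percentage is taken in completers, that patient disappears from it, and the figure describes only those who reached the end of the year.

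Two analysts following the plan could report different primary results from the same data, and the completer version does not show the deaths. The analysis is descriptive with no success threshold, so the stake is a misleading feasibility figure and not a wrong test decision.

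The survival comparison has a different cause. Section 10.3 does not create it. It comes from choosing controls by an outcome, one-year completion, that already implies survival.

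**Working it through.** **The plan's own figures.** The documents give no expected retention, mortality, loss rate or precision target, so there is no retention figure to reproduce. The stated sizes are consistent: 40 + 20 = 60 and 40:20 = 2:1 (Protocol Summary; section 10.5).

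**Inputs.** From the documents: 40 dosed prospective patients. Assumed: s patients switched off drug but followed to 1 year, and d patients who die. The main case takes s = 6.

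**Deaths.**
- All dosed: (40 − s − d)/40
- Completers: (40 − s − d)/(40 − d)

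| d (s = 6) | All dosed | Completers | Difference |
|---|---|---|---|
| 0 | 34/40 = 85.0% | 34/40 = 85.0% | 0 |
| 1 | 33/40 = 82.5% | 33/39 = 84.6% | +2.1 points |
| 2 | 32/40 = 80.0% | 32/38 = 84.2% | +4.2 points |
| 4 | 30/40 = 75.0% | 30/36 = 83.3% | +8.3 points |

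Varying s from 0 to 8 gives a difference of 3.9 to 5.0 points at d = 2 and 7.8 to 10.0 points at d = 4. With s = 0 the completer figure is 100% however many patients die (d = 4: 36/36 against 36/40 = 90.0%).

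At d = 4 the exact 95% intervals are 58.8 to 87.3% for 30/40 and 67.2 to 93.6% for 30/36. The first has a half-width of (87.3 − 58.8)/2, about 14 points. The 8.3-point shift lies inside that, but it is systematic.

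**Withdrawals.** Suppose instead that the 4 removed patients all withdrew and c of them are on Envarsus XR at 1 year. All dosed is (30 + c)/40, and completers stay at 30/36 = 83.3%.

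| c | All dosed | Completers minus all dosed |
|---|---|---|
| 0 | 75.0% | +8.3 points |
| 1 | 77.5% | +5.8 points |
| 2 | 80.0% | +3.3 points |
| 3 | 82.5% | +0.8 points |
| 4 | 85.0% | −1.7 points |

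The sign changes where the share of removed patients still on drug equals the completer rate: 4 × 30/36 = 3.33 of 4. For deaths c is zero, so the direction is fixed. For withdrawals and losses it is not.

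**Survival.** Assume k deaths at distinct times among 40, none among 20 controls, and no earlier censoring. At the j-th death, 41 − j prospective patients and 20 controls are at risk. Expected prospective deaths are the sum of (41 − j)/(61 − j), and the variance is the sum of 20(41 − j)/(61 − j)².

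- k = 2: E = 40/60 + 39/59 = 1.33, V = 0.45, p = 0.314
- k = 4: E = 2.63, V = 0.90, p = 0.149
- k = 8: E = 5.16, V = 1.83, p = 0.036

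In completers of both arms there are no first-year deaths, so V = 0 and the statistic does not exist. In all dosed patients every death falls in the Envarsus XR arm, so observed always exceeds expected.

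**The case against.** The best reply is that a heading is weak evidence, especially in a protocol that still carries unedited template text (section 17 has an unfilled placeholder). The running text suggests that efficacy means something else. The primary objective is feasibility (3.1), and the hypotheses concern ACR, de novo DSA and CLAD (10.2). Section 10.4.4 makes discontinuation a safety endpoint, which 10.3 analyses in everyone dosed. A near-complement of retention is therefore already planned in the wider set.

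This stands in part. The completer denominator is the literal reading, not a certainty. But under the rival reading retention has no assigned set at all, and the discontinuation analysis is neither the primary result nor a rule for counting deaths.

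Three stronger inferences are not supported:
- A reader might infer that the completer set always biases retention upward. Section 5.7.2 lets withdrawn patients stay on Envarsus XR, and the difference can then reach −1.7 points in the case above. The status of lost patients is simply unknown. The vital-status clause in 13.4 covers only revoked authorization and asks for that item as a minimum, so it does not show that drug status will generally be missing.
- A reader might take retention as the plan's only primary result. Section 10.4.1 calls freedom from ACR the primary outcome, which conflicts with 4.2.1 and 10.4.2.
- A reader might conclude that the ACR, CLAD and DSA analyses, or the data requested at withdrawal, must be extended. This defect does not require either.

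**Conclusion.** The point holds in a conditional form and should be fixed. The missing denominator and the missing rule for deaths are plain from the text. If 10.3 is applied to 10.4.2 as the heading implies, each death removed raises the reported percentage as long as some patients are retained. On assumed counts (40 dosed, 6 switched) the rise is 4.2 points with 2 deaths and 8.3 with 4. It is zero if nobody dies, withdraws or is lost. These sizes rest entirely on assumed counts and are not forecasts.

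The survival defect stands separately and follows from sections 5.1 and 10.5. The planned log-rank test is undefined in completers and can only go against Envarsus XR in all dosed patients. A difference there should not be read as evidence of harm, because the controls were selected to have survived.

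**What to change.** **Retention (10.3 and 10.4.2).**
- State that the primary percentage uses all prospective patients who took at least one dose of Envarsus XR.
- Count death, a switch off Envarsus XR, and unknown status at 1 year as not remaining.
- Classify withdrawn patients by their known drug status at 1 year.
- Report the exact 95% confidence interval and the separate counts of deaths, withdrawals and losses.
- Keep the completer figure as supportive.

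**Survival (10.4.3, item 6).** Drop the between-arm test, report 1-year survival of all dosed prospective patients descriptively, and state the selection of controls on one-year completion as a limitation.

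**Consistency.** Reconcile 10.4.1, which names freedom from ACR as the primary outcome, with 4.2.1 and 10.4.2.

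**Cost.** Wording changes only, with no added patients or visits. The retention figure may be less favourable, and the formal survival comparison is lost, though it was not interpretable with this control cohort.

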## **10.4 Description of Statistical Methods**

### **10.4.1**

#### **General Approach**

The study is a two-arm, non-randomized study comparing a prospective arm of patients receiving Envarsus XR to a historical control who received IR tacrolimus. Descriptive statistics will be used for baseline characteristics and to compare nominal outcomes such as de novo DSA and the incidence of CLAD at 1 year post-transplant. These data will be presented as frequencies and will be compared using Chi-square tests or Fishers exact test, as appropriate. The primary outcome freedom from ACR will be compared using Kaplan-Meier survival analysis and analyzed with the log-rank test. Continuous data will be presented as median (interquartile range) and compared using Mann-Whitney U test. A two-tailed P value of < 0.05 will be considered as significant for inferential tests.

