## 3 Objectives and Purpose

### 3.1 Primary Objective

The primary objective will be to assess the feasibility of early conversion to Envarsus XR at 1-year follow-up.

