#### 4.2.2

#### Secondary Study Endpoints

Secondary endpoints will include freedom from ACR at 1-year follow-up, ACR burden at 1-year follow-up as assessed by the composite rejection standardized score (CRSS), treated episodes of rejection, the incidence of chronic lung allograft dysfunction (CLAD) at 1-year, incidence of de novo DSA in the first postoperative year, change in estimated glomerular filtration rate (eGFR) over the first post-operative year, and 1-year survival.

CONFIDENTIAL

This material is the property of the NYU School of Medicine and Langone Medical Center. Do not disclose or use except as authorized in writing by the study sponsor

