### **10.4.3**

#### **Analysis of the Secondary Endpoint(s)**

1. Freedom from ACR will be compared using Kaplan-Meier survival analysis and the log-rank test.
2. Composite rejection standardized score at 1 year follow-up will be presented as median (IQR) and will be compared using the Mann-Whitney U test
3. Treated episodes of rejection will be presented as frequencies and compared using chi-square test
4. Incidence of CLAD at 1 year will be presented as odds ratio with 95% confidence intervals and compared between groups using logistic regression.
5. Incidence of *de novo* DSA at 1 year will be presented as odds ratio with 95% confidence intervals and compared using between groups using logistic regression.
6. Mortality a 1 year post-transplant will be compared using Kaplan-Meier survival curves and log-rank analysis.

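### Section 10.4.1 calls freedom from ACR the primary outcome although the endpoint sections make 1-year retention on Envarsus XR primary, and section 10.2 states the ACR hypothesis in the wrong direction

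*Combined protocol and SAP*

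**What the plan says.** Section 10.4.1 (General Approach) assigns the primary label to rejection: "The primary outcome freedom from ACR will be compared using Kaplan-Meier survival analysis and analyzed with the log-rank test". Two sentences later it adds: "A two-tailed P value of < 0.05 will be considered as significant for inferential tests".

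The sections that define the endpoints say otherwise. Section 3.1: "The primary objective will be to assess the feasibility of early conversion to Envarsus XR at 1-year follow-up". Section 4.2.1: "The primary endpoint will be percentage of patients remaining on Envarsus XR at 1-year follow-up". Section 10.4.2 repeats this ("The primary endpoint, percentage of patients remaining on Envarsus XR at 1-year, will be measured as a single endpoint on a nominal scale") and gives the method: "It will be analyzed using descriptive statistics". Section 4.2.2 places rejection in the second tier ("Secondary endpoints will include freedom from ACR at 1-year follow-up"), and item 1 of section 10.4.3 analyses it there: "Freedom from ACR will be compared using Kaplan-Meier survival analysis and the log-rank test".

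Section 10.2 contains the only statistical hypotheses. Its first sentence expects freedom from ACR in the first year to be reduced under Envarsus XR. Its second expects fewer DSA and CLAD events because rejection will be less frequent. Section 2.4.2 lists a lower ACR burden as a potential benefit. Section 10.2 says nothing about retention.

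Section 10.1 holds that no formal SAP is needed. Section 10.5 plans no power calculation. In the Protocol Summary, the Objectives row puts feasibility first, but the Endpoint row lists only CKD, ACR, AMR and de novo DSA.

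**The concern.** Two adjacent subsections, 10.4.1 and 10.4.2, name different primary outcomes. They lead to different kinds of headline result. One is a descriptive percentage from a single arm. The other is a p-value from an open-label, non-randomised comparison with historical patients. With no separate SAP, section 10 is the operative statistical text, and it could be cited for either result once the data are known.

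The hypothesis that would stand beside an ACR result is also worded backwards. Freedom from ACR is the favourable outcome, so predicting its reduction predicts more rejection. A reader who saw only 10.2, 10.4.1 and the Summary Endpoint row would take rejection to be the study's main question.

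**Working it through.** **Inputs.** Sections 2.4.2, 3.1, 4.2.1, 4.2.2, 5.6, 10.1 to 10.5 and the Protocol Summary. The plan gives no power, event rate or effect size, so there is no statistical figure to reproduce. Its sample sizes are consistent: 40 + 20 = 60 and 40/20 = 2.

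**Step 1: which endpoint is primary.**

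| Section | Retention at 1 year | Freedom from ACR |
|---|---|---|
| 3.1 | primary objective is feasibility | not mentioned |
| 4.2.1 | primary | not mentioned |
| 4.2.2 | not mentioned | secondary |
| 10.4.1 | not mentioned | **primary**, log-rank |
| 10.4.2 | primary, descriptive | not mentioned |
| 10.4.3, item 1 | not mentioned | secondary, log-rank |

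One section conflicts with four endpoint sections and with the primary objective. The ACR method is the same in 10.4.1 and 10.4.3, so the conflict concerns status, not the test.

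**Step 2: direction.** The first sentence of 10.2 says less freedom from ACR, hence more rejection. Its second sentence says less rejection. Section 2.4.2 says a lower ACR burden. The first sentence is the outlier. The test is two-tailed, so its p-value does not depend on the wording.

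**Step 3: what the ACR reading would put forward as primary.** This is an illustration; the hazard ratios and event counts are assumed. For a two-sided 0.05 log-rank test with 80% power and allocation p = 2/3, the events required are (1.960 + 0.842)² / [p(1 − p)(ln HR)²].

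- HR 0.5: 7.85 / (0.2222 × 0.4805) = 73.5, so 74 events
- HR 0.6: 136 events
- HR 0.7: 278 events

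Time to first ACR can give at most 60 events in 60 patients. With 15 to 40 events, power is 24% to 54% at HR 0.5 and 10% to 19% at HR 0.7.

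**Step 4: the retention denominator, a separate question.** Section 10.4.2 is headed as a primary efficacy analysis, and section 10.3 restricts efficacy to patients who complete the first year after transplant. If that restriction applied, patients who left before one year would drop out of the denominator of the measure meant to count them. Section 10.4.4, however, treats discontinuation of therapy as a safety endpoint, and 10.3 runs safety analyses on everyone who took one dose.

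For illustration, assume 32 patients are retained. Only 40 comes from the plan (section 5.6); 32, 36 and 34 are assumptions. The exact (Clopper-Pearson) 95% limits are Beta⁻¹(0.025; x, n − x + 1) and Beta⁻¹(0.975; x + 1, n − x).

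| Denominator | Retained | Exact 95% CI |
|---|---|---|
| 40, all treated | 32/40 = 80.0% | 64.4% to 90.9% |
| 36 completers | 32/36 = 88.9% | 73.9% to 96.9% |
| 34 completers | 32/34 = 94.1% | 80.3% to 99.3% |

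**The case against.** The strongest reply is that the plan already resolves the label. Section 10.4.1 is a general paragraph, while the dedicated sections agree with one another and with the primary objective. No data, test or sample size depends on the label, and a report that led with ACR would contradict 4.2.1 and 10.4.2. The reversal in 10.2 is an evident slip, with freedom from ACR written where ACR was meant. The Summary Endpoint row labels nothing primary. Most of this stands, and it keeps the severity modest. It does not remove the need for correction, because 10.4.1 and 10.2 belong to the only statistical text the study will have.

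A reader might go further and infer that the ACR analysis or its p-value is wrong, or that the study really intends ACR as primary. The documents support neither: the method is identical in both places, the test is two-tailed, and the endpoint sections point to retention.

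A reader might also take the spread from 80% to 94% as the size of the label conflict. It is not. Those figures concern only the denominator and rest on assumed counts; correcting the label would leave them unchanged. Nor does the plan say outright that early leavers are excluded from retention. The heading of 10.4.2 read with 10.3 suggests it, while 10.4.4 read with 10.3 points to all treated patients.

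Finally, omitting a confidence interval contradicts nothing, since descriptive statistics can include one.

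**Conclusion.** The concern holds as an internal inconsistency of modest severity. Section 10.4.1 gives freedom from ACR a primary status that 3.1, 4.2.1, 4.2.2, 10.4.2 and 10.4.3 do not support, and the first sentence of 10.2 reverses the intended hypothesis. Neither changes a computation, so the label conflict has no numerical size. Its consequence lies in reporting: which result may be called primary, and which direction is quoted as the prior expectation.

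The retention denominator is a related but distinct gap. It is unstated, and the completer reading would tend to raise the percentage. How far depends on counts that the plan does not give. The conclusion on label and direction rests on the text alone; the power and interval figures are illustrations under stated assumptions.

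**What to change.** - **10.4.1:** for freedom from ACR, change *primary outcome* to *secondary outcome*.
- **10.2:** for freedom from ACR, change *reduced* to *increased*, and add that the primary aim is to estimate the percentage remaining on Envarsus XR at 1 year.
- **Protocol Summary, Endpoint row:** align with section 4.2, with retention as primary.
- **10.4.2 (denominator, separate from the label):** state that retention is calculated over all prospective patients who took at least one dose of Envarsus XR. Sections 10.3 and 10.4.4 together already apply that set to discontinuation.
- **Optional:** report retention with an exact 95% confidence interval. No hypothesis test or success threshold is needed for a descriptive pilot endpoint.

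The cost is a few sentences and the IRB review that section 13.2 requires for any amendment. No patients, data or procedures are added. The changes should be made before outcome results are examined.

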### **10.4.2**

#### **Analysis of the Primary Efficacy Endpoint(s)**

The primary endpoint, percentage of patients remaining on Envarsus XR at 1-year, will be measured as a single endpoint on a nominal scale. It will be analyzed using descriptive statistics.

